### **Progressive Disease**

PD is defined by at least one of the following compared to pretreatment:

- $\geq 25\%$  increase in the sum of the products of the greatest perpendicular dimensions of at least two lymph nodes by CT or MRI on two consecutive examinations at least 2 weeks apart (at least 1 node must be  $\geq 2$  cm in minimum length) or appearance of new palpable lymph nodes
- $\geq 50\%$  increase in the absolute number of circulating lymphocytes, on two consecutive examinations showing abnormal lymphocytosis at least 2 weeks apart
- $\geq 25\%$  decrease in hemoglobin (must be  $< 11$ g/dL), platelets (must be  $< 100 \times 10^9/L$ ), or ANC (must be  $< 1.5 \times 10^9/L$ ) unless these are judged to be effects of treatment.

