### 11.1 Response Criteria

Following the end of treatment, 6 month post-end of treatment, and interim (during treatment; if applicable) disease assessment, the Principal or Associate Investigator will record the tumor response. Responses include: CR with or without MRD, PR, stable disease (SD), PD, and relapse. The Principal or Associate Investigator will also record the clinical response prior to each treatment cycle, and at each follow-up visit after the 6 month post-end of treatment assessment. PD may only be used during therapy. Once a subject has ended therapy, worsening of disease no longer meeting criteria for best response will be designated as disease relapse. Response criteria will be based on previous HCL studies ([Cheson et al, 1998](#); [Grever et al, 1995](#); [Hoffman et al, 1997](#); [Catovsky et al, 1987](#)). Although the requirements varied slightly among these trials, certain requirements are well accepted and considered standard. Isolated laboratory values not consistent with a response may be ignored in the assessment of a response, at the discretion of the investigator, if preceded and followed by the values for the same laboratory that are consistent with the identified response, or if they occur within the first 12 days of the cycle. The CBC used as a baseline for determining improvement is generally the last one prior to drug, unless that CBC is not representative of others immediately preceding it and is thought to contain lab errors. Response is verified independently through a central disease response assessment vendor to be determined.

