### **Relapse**

- Relapse from CR: Loss of criteria needed for CR, excluding transient decrease in lab values below criteria for CR.
- Relapse from PR: Loss of criteria needed for PR, excluding transient decrease in lab values below criteria for PR.
- Relapse from SD: Patients who meet above criteria for PD when compared to measurements after end of therapy.

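### In Section 11.1 a 25% fall in blood counts needs no mandatory confirmation to count as PD or as relapse from SD, so count variation in stable patients can add false PFS and TTF events

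*Protocol*

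**What the plan says.** All the wording at issue is in Protocol Section 11.1.

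- **PD, nodes and lymphocytes.** Measured nodal growth must be seen "by CT or MRI on two consecutive examinations at least 2 weeks apart". A lymphocyte rise must be seen "on two consecutive examinations showing abnormal lymphocytosis at least 2 weeks apart".
- **PD, cytopenia.** A fall of at least 25% in hemoglobin, platelets or ANC counts if the value is also below 11 g/dL, 100 × 10⁹/L or 1.5 × 10⁹/L respectively. No repeat is asked for. The exemption is "unless these are judged to be effects of treatment".
- **Relapse.** From PR it is "Loss of criteria needed for PR, excluding transient decrease in lab values below criteria for PR", and the CR bullet is built the same way. For SD the text is only "Relapse from SD: Patients who meet above criteria for PD when compared to measurements after end of therapy".
- **Isolated values.** "Isolated laboratory values not consistent with a response may be ignored in the assessment of a response, at the discretion of the investigator". There are two routes to this: the neighbouring results on both sides agree with the response being held, or the odd value arises early in a cycle, up to day 12.

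Elsewhere, relapse and PD are events in PFS (Section 13.4.1.5) and TTF (Section 13.4.1.6). Patients not in CR have a CBC every 3 months for 2 years (Section 3.3.4.3). Section 5.5 takes a patient off study on confirmed progression or relapse but does not say what confirms it.

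**The concern.** Blood counts are the item measured most often in follow-up, and they vary from visit to visit in a patient whose disease has not changed. The authors guarded against this for the other measured PD limbs and for relapse from CR and PR. They did not do so for the cytopenia limb or for relapse from SD. A stable patient checked eight times against a reference that may itself be noisy can cross the 25% line by chance.

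Each such crossing is an early PFS and TTF event that pulls the Kaplan-Meier curve down. Because the one safeguard is optional, two readers could also derive different events from the same counts.

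**Working it through.** **The plan's own figures.** The Protocol gives no rate for false PD or relapse. Its design figure (77 subjects, 90% power, 28% versus 13%) concerns durable CR. It reproduces with the exact binomial test: 17 or more of 77 gives an upper-tail alpha of 0.0189 and power of 0.903. Nothing below touches it.

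**Inputs from the Protocol.** The 25% fall and the three floors (11.1); eight CBCs in 2 years (3.3.4.3); entry on any one of ANC < 1.0, platelets < 100, hemoglobin < 10 or symptomatic splenomegaly (3.1.1).

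**Assumptions not in the Protocol.** Within-patient CVs for ANC/platelets/hemoglobin of 15/8/3%, 20/10/4% or 25/12/5%. Counts are log-normal, independent between visits, with a constant mean (a truly stable patient). There is one reference CBC, and the patient is followed for all eight visits.

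**One look, floor already met.** With σ² = ln(1 + CV²), P = Φ[ln 0.75 / (√2·σ)], where ln 0.75 = −0.2877.
- CV 5%: σ = 0.0500, z = −4.07, P = 0.002%
- CV 10%: σ = 0.0998, z = −2.04, P = 2.1%
- CV 15%: σ = 0.1492, z = −1.36, P = 8.6%
- CV 20%: σ = 0.1980, z = −1.03, P = 15.2%
- CV 25%: σ = 0.2462, z = −0.83, P = 20.4%

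Hemoglobin at 3–5% CV therefore contributes almost nothing. ANC contributes most.

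**Eight looks, floors applied.** Simulation of at least 200,000 patients per case. An event is any lineage at or below 0.75 × its reference and below its floor.

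| Stable patient (mean ANC, platelets, Hb) | Low CVs | Middle CVs | High CVs |
|---|---|---|---|
| All three low (0.8, 70, 10) | 35% | 54% | 67% |
| ANC low only (0.8, 140, 12) | 33% | 49% | 59% |
| Platelets low only (2.5, 70, 12) | 3–4% | 15% | 33% |
| Hb low only (2.5, 140, 9.5) | 0.3–0.4% | 5% | 18% |
| Splenomegaly only (2.5, 140, 12) | 0.3% | 5% | 18% |

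The floors explain the spread. At a mean ANC of 2.5 the count must drop below 1.5, a fall of 1 − 1.5/2.5 = 40%, not 25%.

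**Effect of confirmation (all three low).** A repeat count after each low value gives 12%, 23% and 33%. Applying the existing isolated-value rule every time, approximated as two consecutive scheduled low counts, gives about 10%, 20% and 29%.

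**Effect of the reference.** One lineage with its floor met, eight looks:

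| CV | As written, one reference count | Confirmed, one reference count | Confirmed, mean of 3 reference counts |
|---|---|---|---|
| 10% | 11% | 2% | 0.2% |
| 15% | 33% | 11% | 4% |
| 20% | 49% | 22% | 12% |
| 30% | 64% | 36% | 30% |

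Confirmation against one noisy reference leaves much of the error. Averaging the reference without confirmation does not help at the higher CVs: 48% at CV 20% and 70% at CV 30%.

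**The case against.** The strongest reply is that Section 11.1 already has a safeguard. SD is listed among the responses, so the isolated-value rule can be read to cover it. A single low value bracketed by consistent ones, or falling in the first 12 days of a cycle, may be set aside. A reader might therefore infer from the PD bullet alone that one count always creates an event with no protection, and the Protocol does not support that. What stands is that the rule is optional, is addressed to the investigator, and in follow-up may wait 3 months for the next scheduled CBC.

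Four other points limit the claim.

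- **Reference count.** A reader might infer that the Protocol fixes a single reference count for relapse from SD. It says "Patients who meet above criteria for PD when compared to measurements after end of therapy", which is plural and undefined. The sentence allowing an unrepresentative baseline CBC to be replaced is worded for improvement and needs suspected laboratory error. The single count is a modelling assumption, and the missing definition is a defect in its own right.
- **Central review.** Response is verified by a central vendor, and CBC reports are submitted to it (Sections 11.1 and 13.3). This mitigates the problem, but the vendor is given no confirmation rule for this limb.
- **Size.** The 35–67% range is a near worst-case patient. Entry needs only one criterion, so it should not be read as a rate for the trial. Nor can a number of affected patients be derived: the Protocol gives neither the patient mix nor the share with SD, and follow-up can end early on alternative therapy (Section 5.5).
- **Treatment-effect exemption.** A reader might infer that it lapses once treatment ends. The text sets no time limit, and relapse from SD imports the PD criteria whole. It remains a matter of judgement.

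Finally, PFS and TTF are secondary Kaplan-Meier estimates with no stated test, and Section 13.1 leaves analysis details to the SAP. But the event criteria themselves are fixed in Section 11.1.

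**Conclusion.** The point holds in a limited form. The cytopenia limb of PD has no mandatory confirmation, relapse from SD lacks the transient-decrease exclusion, its reference is undefined, and the only safeguard is discretionary. The effect could be material for PFS and TTF in stable patients with neutropenia: about 33–59% with a false relapse over eight quarterly CBCs. It is smaller with low platelets alone (about 3–33%) and smaller still with low hemoglobin or splenomegaly alone (0.3–18%). These figures rest on CVs that the Protocol does not give, on one reference count, on independent visits and on the optional rule not being used. The asymmetry in the text does not depend on them. The durable CR rate and the sample size are unaffected, so this should be fixed but does not threaten the main conclusion.

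**What to change.** Reconcile the PD, relapse and isolated-value paragraphs of Section 11.1, for endpoint derivation only:

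1. Count the 25% fall as a PFS or TTF event only when it is present on two successive CBCs no less than 2 weeks apart, dated at the first.
2. Give relapse from SD the same exclusion of transient laboratory falls that relapse from CR and PR already has.
3. Make the isolated-value rule binding in central review, and write it into the review charter.
4. Define the reference for relapse from SD, preferably as the mean of several post-treatment CBCs where available. This works together with item 1, not in place of it.

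The cost is a few wording changes, an occasional repeat CBC after a low follow-up count, and an event known about 2 weeks later. No dosing or treatment-stopping rule is proposed.

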### **Stable Disease**

SD will be characterized by not meeting the criteria for CR, PR, or PD as outlined above.

### **Relapse**

- Relapse from CR: Loss of criteria needed for CR, excluding transient decrease in lab values below criteria for CR.
- Relapse from PR: Loss of criteria needed for PR, excluding transient decrease in lab values below criteria for PR.
- Relapse from SD: Patients who meet above criteria for PD when compared to measurements after end of therapy.

## **11.2 Data Collection**

Data will be collected prospectively and entered into [REDACTED] according to the data management plan. The PI is responsible for the collection, maintenance and quality control of study data.

Quality assurance complete records must be maintained on each patient treated on the protocol. These records should include primary documentation (eg, laboratory report slips, X-ray reports, scan reports, pathology reports, physician notes, etc) which confirm that:

- The patient met all eligibility criteria

- Signed informed consent was obtained prior to treatment
- Treatment was given according to protocol (dated notes about doses given, complications, and clinical outcomes)
- Toxicity was assessed according to protocol (laboratory report slips, etc)
- Response was assessed according to protocol (X-ray, scan, lab reports, date noted on clinical assessment, as appropriate)

All data will be kept secure. Personal identifiers will not be used when collecting and storing data. An enrollment log will be maintained in the regulatory binder/file which is the only location of personal identifiers with unique SID number.

## **12 STUDY AND DATA MANAGEMENT**

### **12.1 IRB/IEC Approvals**

The PI will provide the sponsor with a copy of the participating institution's approved continuing review. Registration will be halted at any participating institution in which a current continuing approval is not on file at the IRB/IEC.

### **12.2 Study Agreements**

The PI at each center should comply with all the terms, conditions, and obligations of the Clinical Study Agreement, or equivalent, for this study. In the event of any inconsistency between this Clinical Study Protocol and the Clinical Study Agreement, the terms of Clinical Study Protocol shall prevail with respect to the conduct of the study and the treatment of subjects and in all other respects, not relating to study conduct or treatment of subjects, the terms of the Clinical Study Agreement shall prevail.

Agreements between the sponsor and the PI must be in place before any study-related procedures can take place, or subjects are enrolled.

### **12.3 Archiving of Study Documents**

The Investigator follows the principles outlined in the Clinical Study Agreement.

### **12.4 Training of Study Site Personnel**

A sponsor representative will review and discuss the requirements of the Clinical Study Protocol and related documents with the investigational staff and also train them in any study-specific procedures and system(s) utilized.

The PI will ensure that appropriate training relevant to the study is given to all of these staff, and that any new information relevant to the performance of this study is forwarded to the staff involved.

The PI will maintain a record of all individuals involved in the study (medical, nursing and other staff).

## **12.5 Monitoring of the Study**

During the study, a sponsor representative will have regular contacts with the study site, including visits to:

- Provide information and support to the investigator(s)
- Confirm that facilities remain acceptable
- Confirm that the investigational team is adhering to the protocol, that data are being accurately and timely recorded in the eCRFs, that biological samples are handled in accordance with the Laboratory Manual and that study drug accountability checks are being performed
- Perform source data verification (a comparison of the data in the eCRFs with the subject's medical records at the hospital or practice, and other records relevant to the study) including verification of informed consent of participating subjects. This will require direct access to all original records for each subject (eg, clinic charts)
- Ensure withdrawal of informed consent to the use of the subject's biological samples is reported and biological samples are identified and disposed of/destroyed accordingly, and the action is documented, and reported to the subject.

The sponsor representative will be available between visits if the investigator(s) or other staff at the center needs information and advice about the study conduct.

### **12.5.1 Protocol Deviation**

A protocol deviation is generally an unplanned excursion from the protocol that is not implemented or intended as a systematic change. A protocol deviation may be categorized as major or minor depending on its effect on the risk/benefit; subject's rights, safety, or welfare; and/or on the integrity of the data.

A major protocol deviation generally increases risk or decreases benefit; affects the subject's rights, safety, or welfare; or affects the integrity of the data. Examples include failure to obtain informed consent, obtaining informed consent after initiation of study procedures, failure to report SAE to the IRB or sponsor, and failure to document drug administration. A minor protocol deviation does not increase risk or decrease benefit; does not have a

significant effect on the subject's rights, safety, or welfare; and/or does not have a significant effect on the integrity of the data. Examples include receiving prior radioimmunotherapy between 6 months to 2 years prior to enrollment in study and missing optional visits.

The investigator(s) should document any deviation from the protocol regardless of the reason for the deviation. Only when the protocol was not followed in order to avoid an immediate hazard to the subjects or for other medically compelling reason, the investigator should prepare and submit the records explaining the reasons thereof to MedImmune and the head of study site and retain a copy of the records.

## **13 STATISTICAL CONSIDERATIONS**

### **13.1 General Considerations**

Data will be provided in data listings sorted by subject number and in tabular summaries. Categorical data will be summarized by the number and percentage of subjects in each category. Continuous variables will be summarized by descriptive statistics, including mean, standard deviation, median, minimum, and maximum. Confidence intervals (CIs) will be two-sided, unless otherwise stated. Details of endpoint analyses will be described in the statistical analysis plan.

### **13.2 Analysis Populations**

The intent-to-treat (ITT) subject population will include all subjects who have been entered into the study and treated by moxetumomab pasudotox. The ITT population is the primary population for the efficacy analyses and the summary of baseline characteristics.

The efficacy evaluable subject population will include all subjects who have received at least 1 dose of moxetumomab pasudotox and have a baseline and at least one post baseline disease assessment including bone marrow examination and cross sectional imaging. The evaluable subject population will be identified prior to database lock and will be the secondary population for efficacy analysis.

The safety subject population will include all subjects who receive at least 1 dose of moxetumomab pasudotox.

### **13.3 Primary Endpoint**

The primary objective of this study of moxetumomab pasudotox in relapsed HCL is to determine the rate of durable CR, defined as the proportion of subjects who meet blood, bone marrow, and imaging criteria for CR, followed by a > 180 day duration of HR, with HR

being defined as the blood counts needed for CR. The durable CR rate and its 95% CI will be constructed using the exact probability method (Clopper-Pearson exact interval) in the Intent-to-Treat population. [REDACTED]

[REDACTED] Seventy-seven subjects will provide 90% power to detect a difference between 28% and 13% durable CR rates using 2-sided significance level of 0.05. As a supportive analysis, the durable CR rate and its 95% CI will be estimated based on the evaluable population. [REDACTED]

The central independent review of disease response and disease progression will be the basis for primary analyses. Blinded independent review of response to treatment will be performed by a central vendor. An imaging manual will be distributed to provide guidance to both imaging and study personnel regarding review of scanning parameters and associated activities required for study image collection. Bone marrow slides will be used for response assessment. Images, pathology slides from bone marrow biopsies/aspirates, reports of CBC, and associated documentation must be acquired as instructed in this manual and submitted to the central vendor.

## **13.4 Secondary Endpoints**

The secondary objectives of this study are to evaluate the safety of moxetumomab pasudotox in this subject population, other antitumor activities, PK, and immunogenicity.

### **13.4.1 Other Antitumor Activities**

Other assessments of antitumor activity include rate of CR, objective response (OR), time to response (TTR), duration of CR and OR, and PFS.

#### **13.4.1.1 CR Rate, Duration of CR (Disease-Free Survival), and Duration of Hematologic Remission**

The CR rate is defined as the proportion of subjects that have achieved CR. The 95% CI of the CR rate will be constructed using the exact probability method (Clopper-Pearson exact interval). Duration of CR (also called disease-free survival) will be measured from the first documentation of CR (by imaging, bone marrow biopsy and blood counts) to the time of relapse as defined in Section 11.1. Duration of HR will be measured from the first documentation of CR (by imaging, bone marrow biopsy and blood counts) to the time of loss of HR. Duration of CR will be censored on the date of the last disease assessment or clinical

response assessment for subjects who have no documented relapse prior to data cutoff, dropout, or the initiation of alternative anticancer therapy. Duration of HR will be censored on the date of the last evaluable hematologic assessment for subjects who have no documented loss of HR prior to data cutoff, dropout, or the initiation of alternative anticancer therapy. The proportion of subjects with a CR and HR at certain time points (eg, 6 month, 1 year, or 2 year) and the median duration of CR and HR may be estimated, if feasible, for the subgroup of subjects with CR using the Kaplan-Meier method. It should be noted that CR duration, which may be shorter than HR duration, is a secondary endpoint and will be summarized separately.

#### **13.4.1.2 Objective Response Rate**

Objective response rate is defined as the proportion of subjects with CR or PR. The 95% CIs of ORR will be estimated using the exact probability method.

#### **13.4.1.3 Time to Response**

Time to response will be measured from the start of moxetumomab pasudotox administration to the first documentation of response (CR or PR). Descriptive statistics of time to response (median, minimum, and maximum) will only be summarized for subjects who have achieved objective response.

#### **13.4.1.4 Duration of Objective Response**

Duration of objective response will be measured from the first documentation of objective response to the event of relapse as defined in Section 11.1. Duration of objective response will be censored on the date of last disease assessment for subjects who have no documented relapse prior to data cutoff, dropout, or the initiation of alternative anticancer therapy. Duration of objective response will be summarized descriptively by using minimum and maximum of duration of objective response observed at a certain follow-up period. The proportion of subjects with response at certain time points (eg, 6 month, 1 year, or 2 year) and the median duration of response may be estimated, if feasible, for the subgroup of subjects with objective response using the Kaplan-Meier method.

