#### **13.4.1.5 Progression-Free Survival**

PFS is measured from the start of moxetumomab pasudotox administration to relapse, PD, or death from any cause. Relapse is considered post-end of treatment when patients no longer meet criteria required for their best response (Section 11.1). PFS will be censored on the last hematologic assessment for subjects without relapse, PD, or death. PFS will be evaluated using the Kaplan-Meier method.

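### Duration of response ends only at relapse, so on one of two readings a responder who progresses on treatment is censored rather than counted

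*Protocol*

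**What the plan says.** Section 13.4.1.4 gives duration of objective response a single end event: "Duration of objective response will be measured from the first documentation of objective response to the event of relapse as defined in Section 11.1". It then "will be censored on the date of last disease assessment for subjects who have no documented relapse" before data cutoff, dropout or new anticancer therapy. PD is not mentioned. Duration of CR in Section 13.4.1.1 also ends at relapse alone.

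The introduction to Section 11.1 divides the two labels by time. For the treatment period: "PD may only be used during therapy". For the period afterwards: "Once a subject has ended therapy, worsening of disease no longer meeting criteria for best response will be designated as disease relapse". Section 13.4.1.5 repeats the second half: "Relapse is considered post-end of treatment when patients no longer meet criteria required for their best response".

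The other time-to-event endpoints name both labels. For PFS: "PFS is measured from the start of moxetumomab pasudotox administration to relapse, PD, or death from any cause". Time to treatment failure (Section 13.4.1.6) also lists relapse and PD as separate events.

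**The concern.** A response can start and be lost while treatment is still running. Treatment lasts up to 6 cycles, clinical response is recorded before each cycle, PR needs no marrow examination, and CR can be documented at the optional interim assessment. If worsening on treatment is called PD and never relapse, a responder with PD in a later cycle has no duration event and leaves the risk set as though still responding. These are the shortest responses. Censoring them inflates the Kaplan-Meier duration, and the same PD is a failure in the PFS analysis. Duration of response is a named secondary objective (Section 1.2) of a trial that Section 2.2 calls pivotal, so its event should not depend on how one word is read.

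**Working it through.** **1. Event lists side by side**

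| Endpoint | Relapse | PD | Death |
|---|---|---|---|
| Duration of objective response (13.4.1.4) | yes | not listed | not listed |
| Duration of CR (13.4.1.1) | yes | not listed | not listed |
| PFS (13.4.1.5) | yes | yes | any cause |
| Time to treatment failure (13.4.1.6) | yes | yes | disease-related |

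If relapse already covered PD on treatment, PFS and time to treatment failure would not need a separate PD term.

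**2. One patient, two readings.** Take a PR documented in an early cycle, followed by PD in a later cycle.
- *Relapse is post-treatment only* (Section 11.1 introduction; Section 13.4.1.5): no relapse exists, so the subject is censored at the last disease assessment.
- *Relapse is loss of CR or PR criteria at any time* (the Relapse definitions in Section 11.1 read alone): the subject has an event once PR criteria are lost.

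A later relabelling as relapse is not secured. Section 5.5 makes confirmed progression an off-study criterion, and Section 3.3.4.1 follows only SD, PR and CR to relapse. Section 5.3, on the other hand, keeps discontinued subjects on the Table 10-2 assessments. Any event picked up that way would be dated late.

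**3. Who is exposed.** Where nodes, liver or spleen were abnormal at baseline, PR needs CT or MRI. Section 11 schedules imaging at screening, end of treatment and 6 months later, so many responses can be fully documented only once treatment is over. CR without MRD stops treatment (Sections 5.3 and 11). That leaves mainly PR documentable without imaging, and CR with MRD at an interim assessment with treatment continued.

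**4. Size.** The protocol gives no figure for duration of response and no rate of on-treatment PD among responders, so every input here is assumed. Let f be the share of responders with on-treatment PD and R(t) the proportion of the others still in response at time t. If the others have no event while on treatment:
- PD counted as an event: (1 − f) × R(t)
- PD censored: R(t)
- Difference: f × R(t)

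Assume the others start to relapse at month 5 of response, exponentially, with a median of 36 months from then. Then R(12) = exp(−ln 2 × 7/36) = 0.874.

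| f | PD counted | PD censored | Difference |
|---|---|---|---|
| 0% | 0.874 | 0.874 | 0 |
| 5% | 0.95 × 0.874 = 0.830 | 0.874 | 0.044 |
| 10% | 0.90 × 0.874 = 0.787 | 0.874 | 0.087 |
| 15% | 0.85 × 0.874 = 0.743 | 0.874 | 0.131 |

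A second set of assumptions was simulated with 200,000 responders: PD uniform over months 1 to 4 of response, the others relapsing exponentially from the start of response, and no other censoring. With f = 5%, the 12-month proportion is 0.475 counted against 0.504 censored (median 12 months for the others), or 0.673 against 0.711 (median 24 months). That is a gap of 3 to 4 points.

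For scale, 75% of 77 subjects is about 58 responders (Section 2.2 gives 72-81% for the predecessor drug), and 5% of 58 is about 3 patients.

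**5. Primary endpoint.** Durable CR rests on CR followed by maintained blood counts and does not use this event. Its sample size reproduces: with 77 subjects, an exact binomial rule of at least 17 durable CRs has an upper tail of 0.0189 at 13% and power of 0.903 at 28%. Nothing here changes that.

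**The case against.** The strongest objection is textual. A reader might infer that relapse, by definition, exists only after treatment. The documents do not settle that. Section 13.4.1.4 points to Section 11.1, where the Relapse definitions for CR and PR are simply loss of the relevant criteria, transient falls aside. Only the SD definition is tied to measurements after therapy. The paragraph on Complete Response Duration also sets no time limit. This stands, and it limits the point to a conflict between two readings. It does not remove the conflict, because the introduction to Section 11.1 and Section 13.4.1.5 pull the other way. Nor would the second reading catch every case. New palpable nodes in a PR patient whose nodes were normal at baseline are PD, yet they need not breach any PR criterion.

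A reader might also infer a wider gap: PD is judged against baseline ("PD is defined by at least one of the following compared to pretreatment"), so a large on-treatment loss of response that stays short of PD would have no event until therapy ends. That holds only on the post-treatment reading; the PR relapse definition taken alone would count it. It does not justify rewriting Section 11.1. The PD criteria exclude falls in counts judged to be treatment effects, and a general rule counting any non-transient on-treatment loss could score drug-related cytopenias as lost response.

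The remaining objections concern weight, and they stand. The exposed group is narrow, the size is assumed, and the endpoint is secondary and descriptive, with Kaplan-Meier estimates planned only if feasible. Section 13.1 leaves details to the statistical analysis plan. Here, however, the protocol itself fixes the event and the censoring rule, so the mismatch lies in the protocol.

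**Conclusion.** The point holds as a correctable inconsistency in a secondary endpoint. Section 13.4.1.4 omits PD while PFS and time to treatment failure include it, and Section 11.1 supports two readings with different results. On the post-treatment reading, censoring on-treatment PD is informative and biases the duration estimate upward whenever any responder progresses on treatment. The size cannot be derived from the protocol: zero with no such patients, and about 4 points at 12 months if an assumed 5% of responders are affected. The larger shares in the table are illustrations with no support in the documents. The affected group is probably small. Duration of CR shares the wording but is less exposed, because CR without MRD ends treatment. The primary endpoint, its sample size and its power are untouched.

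**What to change.** In Section 13.4.1.4, define the event as relapse or PD, and censor only subjects with neither. Make the same change in Section 13.4.1.1 for consistency. Leave the response criteria in Section 11.1 as they are.

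This makes on-treatment PD an event on either reading and brings its handling into line with PFS. It does not make the two endpoints identical, since PFS also counts death, and it does not settle how an on-treatment loss of response short of PD is classified.

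The cost is a short phrase in each of two paragraphs, with no new data. The duration estimate may come out slightly less favourable.
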